## **Stage 2: Preliminary Implementation and Further Refinement**

**Aim 2.** Conduct an initial open trial of this intervention with short-term (4-week) follow-up, and then modify based on feedback and outcomes.

1. We will conduct an open trial of our FMI intervention (friend dyads n=10, 20 women) and comprehensively evaluate the intervention via multiple methods (investigator observations, open-trial sessions, feedback interviews) during and post-intervention.
2. We will use feedback from the open trial to further refine the FMI intervention.

## **Stage 2: Specific Procedures for Preliminary Implementation and Evaluation**

### ***a. Open Trial & Short-Term Follow-Up***

*Open Trial:* We will conduct an open trial (N=10 dyads) of the FMI. Open trial eligibility will be determined using procedures outlined above (see **Screening & Recruitment**). Trained clinical Ph.D. students will conduct these sessions. At the end of each session, participants will give both structured (self-report measures) and semi-structured (interview) feedback regarding their impressions of the intervention. Note that the facilitator who gathers feedback will be different from the FMI interventionist. Participants will have the option to complete all the online questionnaires prior to coming in for their session (within a week of their session).

Immediately following the completion of the intervention, doctoral-student facilitators will present open-ended questions to the friend dyad about each of the content domains of the intervention. The goal will be to stimulate a conversation between dyad members about their perceptions of the intervention. Specifically, these dyad interviews will be used to gather information on two critical aspects of the intervention that we have developed: (1) whether the intervention is seen as personally relevant with regard to the risks women confront and how they may minimize these risks and (2) whether the FMI material is perceived as being feasible to implement in a real world risk environment. As part of this, we will elicit feedback on the extent to which the intervention adequately addresses barriers to helping, including effects of alcohol consumption. We will also solicit information on additional potential barriers to helping behavior not currently addressed in the FMI. This feedback data will be used in concert with investigator and consultant input to further refine the FMI.

*Short-term Follow-up.* Participants in the Open Trial also will be asked to implement the skills and safety plan developed in the intervention over a four-week period. After which they will participate in a follow-up interview. Prior to completing the follow-up interview, participants will complete online self-report measures. These measures may be completed prior to the session (within a week of the session). Dyad members will be interviewed first separately, then together. The objective of this follow-up will be to evaluate participant experiences of implementing the intervention material. All interviews will be conducted by a doctoral-level trainee. This feedback will be semi-structured, and will ask largely about issues pertaining to the implementation of intervention skills in a real-world setting, whether friends used any strategies to protect one another that were not covered in the intervention and how effective they perceived these strategies to be. We also will discuss how alcohol consumption may have influenced implementation of skills learned in the FMI. Finally, we will query about potential iatrogenic effects. Participants who are unable to come in for an in-person follow-up (due to extraneous circumstances), will be offered the opportunity to complete the follow-up via teleconferencing (using Zoom).

We also will elicit systematic feedback from interventionists regarding the implementation of the intervention (e.g., perceptions regarding participant response, etc.). This feedback will be derived from group-based interviews with interventionists, conducted at the end of the open trial.

*Remuneration.* Open Trial participants will be paid \$50 for participating in the intervention and feedback sessions. They will receive an additional \$10 bonus if the pair is scheduled for an appointment within 72 hours of being contacted for scheduling. For pairs who are completing the follow-

up via teleconferencing, they will be paid using the phone application Venmo or with an Amazon gift card (depending on their choice).

**b. Further Refinement**

In this stage, feedback from assessment and the post-session interviews will be aggregated, analyzed, and used to refine the FMI intervention. All intervention sessions in the open trial will be digitally recorded and transcribed. Transcripts of the post-session semi-structured interviews will be created by an RA within a week of the interview. An encrypted audio file will be distributed to investigators to enable them to review feedback independently and then meet to discuss impressions. Three sessions will be selected randomly and distributed to consultant [name], who will review sessions and provide written feedback regarding modifications.

Information gathered from the Open Trial will be used to refine intervention elements as well as procedures for training, recruitment, and adherence materials. Investigators and consultant [name] will continue to meet monthly to discuss emerging impressions, reactions to feedback, and ideas for modification. When all open trial and follow-up sessions are completed, we will hold an Investigator and Consultant meeting. At this meeting, we will synthesize qualitative and quantitative feedback and finalize plans for revising the FMI protocol. If warranted, based on participant feedback and the extent of the revisions, a second open trial with new dyads will be carried out to further refine the FMI intervention protocol.

**Stage 3: Intervention Testing**

**Aim 3.** Conduct a mini-trial with 3-month follow-up via weekly assessments to examine changes in target attitudes (readiness, barriers) and behaviors (friend-based assault prevention behavior skills). We also will examine knowledge and strategies pertaining to the role of alcohol in helping behavior, and will test whether drinking influences the implementation and efficacy of this intervention.

Twenty-four friend dyads will participate in the FMI along with 24 wait-list control dyads (total of 48 dyads). We will compare groups on outcomes at post-intervention and at bi-weekly 3 month follow-ups, and also examine within subjects change. Given the pilot nature of the R34 mechanism and the smaller sample size, we will focus on whether effects are in the expected direction and whether the strength of effect sizes are of practical magnitude. We expect participants receiving the FMI to demonstrate significant increases in readiness, and engagement in FAPBs and alcohol strategies, and decreases in perceived barriers (improved self-efficacy, relationship concerns), at post-intervention and over the 3-month follow-up. We will also use our follow-up data to provide a rich description of the role of alcohol in implementing FAPBs, and whether the FMI reduces the impact of alcohol use. In exploratory analyses, we will examine whether the intervention may be associated with decreased assault risk, as well as decreased drinking (see **Data Analysis Plan**).

**Stage 3 Procedures:**

*Intervention: FMI Mini-Controlled Trial with Intensive Follow-Up*

In this stage, we will test the finalized FMI (see **Screening, Eligibility, and Recruitment** above). To do this, we will contrast outcomes among those in this trial (N=24 dyads) with 24 pairs of friend dyads (total dyad N=48) who are randomly assigned to a wait list control condition.

The FMI will consist of a single session. Sessions will be offered on many days and times across the week to accommodate variability in student schedules. Each session will begin with a baseline assessment. In this session, women will be provided with the refined intervention protocol and will have the opportunity to role play and practice implementing the skills and strategies. Following the intervention, participants will be encouraged to utilize the skills and strategies presented in the intervention over the next 12 weeks, whenever they are out with their friend in a social context.

Dyad pairs assigned randomly (stratified on drinking levels, sexual assault history, and age) to the wait list control condition will be assessed once at baseline and again 12 weeks post-baseline. Assessment measures (baseline, 12 weeks) will mirror those administered to women in the FMI condition. At the completion of the 12 week “wait list,” participants will be administered the FMI and followed for 12 weeks. Comparison of outcomes across conditions will allow for stronger inferences about the efficacy of the intervention, will allow for examination of measurement reactivity, and will increase our sample size to examine within person change.

*Follow-up Assessments.* We will conduct bi-weekly online post-intervention assessments (with the first assessment to occur within 2 weeks of FMI completion) for 12 weeks. The bi-

weekly structure will optimally capture women's experiences applying strategies from the intervention. Participants will be reminded of follow-up assessments by phone, text, and email prompt. Individual members of the dyad will be interviewed in the unlikely event that the other member is lost to follow up over the brief follow-up period. At the end of the 12 weeks, participants will be contacted for an exit interview.

*Stakeholder interviews.* In this second set of stakeholder interviews, we will gather information to inform next steps for the FMI intervention. To this end, a series of 5 interviews (2 randomly selected from prior interviews, 3 new to the project) will be conducted with campus administrators at Buffalo-area colleges. Selection will follow procedures outlined in Stage 1. In these interviews, the final FMI manual will be presented, and feedback would be solicited regarding ideas for scaling the FMI to other populations and contexts.

*Remuneration.* Students will receive electronic gift card payments of \$40 for the baseline assessment (which occurs just prior to the intervention) and \$20 for each post-intervention assessment. To encourage participant retention, participants who complete at least 4/6 bi-weekly assessments will receive a \$20 bonus. Stakeholders will receive \$25 in cash as a gesture of appreciation for participation.

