*Outcome analyses.* The primary goals of Aim 3 are to evaluate whether (1) FMI increases readiness, reduces perceived barriers, and increases alcohol knowledge and strategies post-intervention and over the follow-up (2) FMI increases the implementation of friend-based assault-protective behaviors (FAPB) in our 3-month follow-up, and (3) changes in readiness, perceived barriers, alcohol knowledge and strategies are associated with implementation of FAPDs at 3-month follow-up (potential mechanisms). We will also examine if quality of the dyad relationship changes as a function of the intervention. Increases would suggest strengthening of the relationship as a function of the intervention, and declines would indicate iatrogenic effects. Whether increases in implementation of behavioral strategies are associated with reduced rates of sexual victimization will also be examined. Examination of sexual victimization is exploratory, as victimization rates are expected to be relatively low over the short follow-up period (i.e., approx. 30% across 3 months; Parks et al., 2008). In secondary analyses, parallel analyses will also be done with alcohol use as an outcome variable. Given the pilot nature of the R34 mechanism and the smaller sample size, we will focus analysis on effect sizes and whether effects are in the proposed direction. Effect size estimates can be unreliable in small pilot studies (Kraemer et al., 2006); thus, we will report effect sizes ranges (95% confidence bands).

A prominent feature of our design is that individuals are nested within dyads, and this necessitates a data analytic approach that can accommodate nested data structures. Hence, our Aim 3 analyses are built around hierarchical linear models (HLMs). First, we will evaluate group differences on variables from our first post-intervention assessment (i.e. perceived barriers, readiness, alcohol knowledge and strategies, and implementation of FAPBs) using a two level model (individuals nested within dyads). Treatment will be dummy coded (FMI vs. waitlist control group) and included as a level two covariate. Second, we will utilize all data from our three month follow-ups and repeat these analyses using a three-level model (6 repeated measures nested within individuals, and individuals nested within dyads). In these models treatment will be included as a level three covariate. We will use  $\beta$  to describe effect sizes (Cohen, 1988; Selya et al., 2012).

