A prominent feature of our design is that individuals are nested within dyads, and this necessitates a data analytic approach that can accommodate nested data structures. Hence, our Aim 3 analyses are built around hierarchical linear models (HLMs). First, we will evaluate group differences on variables from our first post-intervention assessment (i.e. perceived barriers, readiness, alcohol knowledge and strategies, and implementation of FAPBs) using a two level model (individuals nested within dyads). Treatment will be dummy coded (FMI vs. waitlist control group) and included as a level two covariate. Second, we will utilize all data from our three month follow-ups and repeat these analyses using a three-level model (6 repeated measures nested within individuals, and individuals nested within dyads). In these models treatment will be included as a level three covariate. We will use  $\beta$  to describe effect sizes (Cohen, 1988; Selya et al., 2012).

Our burst design provides a rich opportunity to examine whether changes in target constructs of interest (e.g., barriers, skills, alcohol knowledge and strategies) are associated with implementation of FAPBs. For these analyses we will combine the post-intervention data from our FMI and WLC groups after the latter has completed the intervention and follow-up assessments. Combining groups will increase our sample size and provide more stable estimates of effect sizes. For these analyses we will include reports of past week protective behavioral strategies just prior to the intervention and weekly aggregates of variables of interest from our three-month follow-up yielding 7 repeated measures nested within individuals and individuals nested within dyads. Time will be included as a level-1 covariate, and we will

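### The randomised comparison is specified at time points where the wait-list arm has no untreated data; only week 12 is observed in both arms

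*Combined protocol and SAP*

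**What the plan says.** **Schedule.** Under Stage 3 Procedures (protocol Section 4), dyads allocated "to the wait list control condition will be assessed once at baseline and again 12 weeks post-baseline". The next sentence gives the same two occasions again. These dyads then receive the FMI and are followed for 12 weeks. The FMI arm has its baseline at the start of the intervention session, then bi-weekly online surveys for 12 weeks, "with the first assessment to occur within 2 weeks of FMI completion". The same section says that comparing the conditions "will allow for examination of measurement reactivity".

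**Analysis.** The Stage 3 aim states: "We will compare groups on outcomes at post-intervention and at bi-weekly 3 month follow-ups". Protocol Section 16.1 (Aim 3) and the SAP then give two FMI-versus-wait-list models:

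- Model 1, two levels: "we will evaluate group differences on variables from our first post-intervention assessment".
- Model 2, specified as a "three-level model (6 repeated measures nested within individuals, and individuals nested within dyads"). On covariates: "In these models treatment will be included as a level three covariate".

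The SAP sentence "Time will be included as a level-1 covariate" belongs to a later analysis that pools both arms after the wait list has crossed over.

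**Measures.** Section 10.3 collects alcohol knowledge only at baseline, post-intervention and 12 weeks; alcohol strategies are also collected bi-weekly.

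**The concern.** Before crossover the wait-list arm has one follow-up, at week 12. Model 1 therefore has no concurrent control. Model 2 can be fitted, but it compares FMI data averaged over weeks 2 to 12 with wait-list data from week 12 alone. Any change over a semester in drinking, going out or survey response then enters the treatment coefficient.

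Using the wait-list women's own bi-weekly surveys does not help, because those follow their FMI session and are treated data. The within-person effect sizes planned in the SAP have no control group, so they cannot stand in for the randomised comparison.

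The plan makes the size and direction of effects its main product. A shifted or reversed effect size would damage that product directly.

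**Working it through.** **Inputs.** 24 dyads per arm, so 48 women per arm (Stage 3: Intervention Testing). FMI follow-ups are taken at weeks 2, 4, 6, 8, 10 and 12, and the wait-list follow-up at week 12 (Stage 3 Procedures). Section 16.2 uses 88 women, or 44 per arm. The documents give no drift and no variance components; both are assumed below.

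**1. Data available to each model**

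| | FMI | Wait list, untreated |
|---|---|---|
| Model 1, women (96 in total) | 48 | 0 |
| Model 2, rows (96 in total) | 48 × 6 = 288 | 48 × 1 = 48 |
| Model 1, women (88 in total) | 44 | 0 |
| Model 2, rows (88 in total) | 44 × 6 = 264 | 44 × 1 = 44 |

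**2. Bias with no treatment effect.** Let D be a linear change from baseline to week 12, in SD units, positive for improvement.

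- Model 2: the mean FMI week is (2+4+6+8+10+12)/6 = 7, and the wait-list week is 12. Bias = (7 − 12)/12 × D = −0.417D.
- Model 1, if the wait-list week-12 value is substituted: (2 − 12)/12 × D = −0.833D.

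| D (assumed) | Model 2 | Model 1, substituted |
|---|---|---|
| 0.1 | −0.04 | −0.08 |
| 0.3 | −0.125 | −0.25 |
| 0.5 | −0.21 | −0.42 |

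A worsening trend reverses the sign and favours the FMI.

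A simulation (600 runs, variance shares of dyad 0.3, woman 0.3 and residual 0.4, tests on dyad means) agrees. At D = 0.5, false rejection at the 5% level was about 38% for model 1 with substitution, 12.5% for model 2 and 5% for a week-12 comparison. At D = 0.2 the rates were about 10%, 5.5% and 5%.

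**3. Would adding week repair model 2?** There are seven observed arm-by-week means (six FMI, one wait list). Intercept, treatment and five week indicators make seven fixed effects. With complete data the treatment coefficient then equals the week-12 difference. Reading it as an effect over six waves assumes a constant effect. A full treatment-by-week model has 12 columns but rank 7, so effects at weeks 2 to 10 are not estimable.

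**4. Precision.** Variance of a dyad mean, with shares 0.3/0.3/0.4:

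- one occasion: 0.3 + 0.3/2 + 0.4/2 = 0.65
- mean of six occasions: 0.3 + 0.3/2 + 0.4/12 = 0.483
- covariance with baseline: 0.3 + 0.3/2 = 0.45

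Standard errors with 24 dyads per arm:

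- Model 2, no time term: √((0.483 + 0.65)/24) = 0.217
- Week 12, unadjusted (equivalently model 2 with categorical week): √(2 × 0.65/24) = 0.233
- Week 12, baseline-adjusted: residual variance 0.65 − 0.45²/0.65 = 0.338, so √(2 × 0.338/24) = 0.168

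With a woman's baseline correlation of only 0.3 (shares 0.3/0/0.7), baseline-adjusted week 12 gives √(2 × (0.65 − 0.3²/0.65)/24) = 0.206. Model 2 without time gives √((0.358 + 0.65)/24) = 0.205.

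**5. Survey exposure.** By week 12 the FMI arm has completed five earlier follow-up surveys and the wait list none. Reactivity to repeated surveys therefore cannot be separated from the FMI effect, even at week 12.

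**The case against.** - **The schedule itself is in conflict.** Section 10.3 describes Stage 3 collection as baseline plus bi-weekly without distinguishing arms, so the count of 48 against 0 depends on which text governs. This is fair as far as it goes. But the wait-list schedule is explicit and given twice, and the bi-weekly surveys are described as post-intervention. Nothing gives the wait list surveys while it waits.
- **Model 2 does not exclude time.** The SAP is silent rather than prohibitive, and it does allow covariates for baseline imbalance. The confounding is also partial, because week 12 is a valid randomised contrast. All true, but imbalance covariates do not remove change over time, and adding week turns model 2 into the week-12 comparison.
- **The precision comparison is not like for like.** Baseline adjustment would also help model 2: its standard error without time falls to √((0.172 + 0.338)/24) = 0.146, below 0.168. This stands, but that model remains exposed to drift and is not the one written.
- **Drift is assumed.** With zero drift there is no bias, and at 0.1 to 0.3 SD the model 2 bias is under 0.6 of its standard error. The substitution in model 1 is nowhere proposed. This limits the size of the bias, but model 1 lacks controls whatever the drift.
- **Reactivity.** Untreated wait-list change from baseline to week 12 says something about response to the baseline assessment, though mixed with time. A narrowed claim could survive.
- **It is a pilot.** Direction and effect size with 95% bands take priority over significance. That makes the bias more relevant, since the effect size is the deliverable.

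**Conclusion.** The concern holds and should be fixed before Stage 3 is analysed. As written, model 1 cannot be run on concurrent data, and model 2 mixes the FMI effect with change over 12 weeks. The absence of wait-list data at weeks 2 to 10 follows from the stated schedule and needs no assumption. The size of the bias does: 5/12 of the drift in model 2, and 10/12 in model 1 if week 12 is substituted, both assuming linear drift and a first survey at week 2. A sound week-12 contrast is already planned in both arms. Under the variance shares examined, adjusting it for baseline costs essentially no precision against model 2 as written.

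**What to change.** **Option 1, wording only.** In Stage 3 Procedures, Section 16.1 and the SAP:

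- Define the randomised contrast as week 12 in both arms, in a two-level model (women within dyads) adjusted for the baseline value.
- Use the same look-back period in both arms at week 12. Section 10.3 refers to the time since the last assessment in one place and to the prior week in another. The former would mean 12 weeks for the wait list and 2 for the FMI arm.
- Report the FMI bi-weekly data as within-arm trajectories.
- State that unequal survey exposure remains, and withdraw the measurement-reactivity claim or limit it to describing untreated wait-list change.

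This needs no new data. The early between-group contrast is lost and the exposure difference stays.

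**Option 2, more data.** Give the wait list the same six online surveys during the wait, and include week in model 2. Both models then become estimable for outcomes collected bi-weekly, and survey exposure is equal. If the Stage 3 payment rates apply, five extra surveys cost 48 × 5 × $20 = $4,800, plus up to 48 × $20 = $960 if the retention bonus is offered. Staff time and participant burden are extra. This has to be settled before wait-list dyads start their wait.

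Under either option, analyse alcohol knowledge only at the waves where it is collected, and not as a six-measure outcome.

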#### **Bi-Weekly Follow-Up Assessment**

**Overview:** Bi-weekly, participants will report on any occasion since the last assessment that the participant was out with the target friend in a social setting. For each such occasion, we will collect information about the context of these occasions (i.e., bar, party, out to dinner), whether there was alcohol, who was present, and whether there was an opportunity for intervention.

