## **24.0 Compensation for Participation**

25.1 *Describe the amount and timing of any compensation to subjects, including monetary, course credit, or gift card compensation.*

*Study 1 Remuneration.* Women will be compensated for focus group participation with \$50 in cash. Stakeholders will receive \$25 in cash as a gesture of appreciation.

*Study 2 Remuneration.* Open Trial participants will be paid \$50 in cash for participating in the intervention and feedback sessions. They will receive an additional \$10 bonus if the pair is scheduled for an appointment within 72 hours of being contacted for scheduling.

*Study 3 Remuneration.* Students will receive electronic gift card payments of \$40 for the baseline assessment (which occurs just prior to the intervention) and \$20 for each post-intervention assessment. To encourage participant retention, participants who complete at least 4/6 bi-weekly assessments will receive a \$20 bonus. Stakeholders will receive \$25 in cash as a gesture of appreciation for participation.

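### The claim that the Stage 3 arm comparison can examine measurement reactivity is unsupported, and the wait-list survey schedule needs reconciling

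*Combined protocol and SAP*

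**What the plan says.** Protocol section 4, Stage 3 Procedures, gives the only explicit wait-list schedule: control dyads "will be assessed once at baseline and again 12 weeks post-baseline". For content, "Assessment measures (baseline, 12 weeks) will mirror those administered to women in the FMI condition". When the wait ends, "participants will be administered the FMI and followed for 12 weeks".

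The intensive follow-up is tied to the intervention: "We will conduct bi-weekly online post-intervention assessments (with the first assessment to occur within 2 weeks of FMI completion) for 12 weeks". Section 24.0 confirms that there are six of these surveys: "participants who complete at least 4/6 bi-weekly assessments will receive a \$20 bonus".

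The same Stage 3 text says that the comparison across conditions "will allow for examination of measurement reactivity". Neither the analysis plan in protocol section 16.1 nor the Statistical Analysis Plan contains a reactivity analysis.

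Other text points to a different schedule. The Stage 3 aim says the groups will be compared at the bi-weekly follow-ups. Section 16.1 and the SAP fit a three-level model to six repeated measures with treatment as a covariate. Both need bi-weekly data from the wait list, which Stage 3 Procedures does not provide.

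**The concern.** The surveys ask about the target behaviours in detail. Each covers every outing with the friend and includes a 49-item bystander scale. For drinking occasions there is also a 24-item protective-strategy questionnaire. Both instruments are answered for what the woman did for her friend and for what the friend did for her (section 10.3). Repeated questioning of this kind could plausibly raise the behaviours it asks about.

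If only FMI women are questioned this way before week 12, any such rise is counted as part of the FMI effect at that visit. Section 16.2 says the trial's main product is effect sizes to inform later studies. A later trial with a different survey load would then plan on an effect that belongs partly to the surveys, and the protocol's sentence would suggest that this possibility could be checked.

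**Working it through.** This is a question of what the design can identify. The plan gives no figure to reproduce.

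**Inputs.** Allocation: "Twenty-four friend dyads will participate in the FMI along with 24 wait-list control dyads (total of 48 dyads"). There are six bi-weekly surveys over 12 weeks (12 / 2 = 6), so five precede the week-12 one. The wait list has baseline and week 12 only, then the FMI and its own 12 weeks of follow-up.

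**Exposure under Stage 3 Procedures as written.**

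| Group and time | FMI | Bi-weekly surveys |
|---|---|---|
| FMI arm, baseline | no | no |
| FMI arm, week 12 | yes | yes |
| Wait list, baseline | no | no |
| Wait list, week 12 | no | no |
| Wait list, 12 weeks after its own FMI | yes | yes |

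The two exposure columns are identical in every row.

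**Week-12 contrast.** Let m be the baseline level, t the change over 12 weeks, F the FMI effect and R the effect of the bi-weekly surveys.

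- FMI arm: m + t + F + R
- Wait list: m + t
- Difference: F + R

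With columns for intercept, FMI and surveys, the design matrix has rank 2 for 3 parameters. For illustration, an observed difference of 0.5 SD fits F = 0.5 with R = 0, F = 0.3 with R = 0.2, and F = 0 with R = 0.5 equally well.

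**Adding more of the data.** Using baseline and week 12 in both arms with a time term gives rank 3 of 4. Adding the wait list after its own FMI (m + 2t + F + R, taking time as linear) still gives 3 of 4, because F and R occur only as a sum.

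**If the wait list is surveyed bi-weekly as well.**

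- FMI arm: m + t + F + R
- Wait list: m + t + R
- Difference: F

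The FMI contrast is now free of survey load, but R cancels and the rank for intercept, FMI and surveys is still 2 of 3. The wait list's own change is t + R, which is reactivity mixed with time. Separating R would need untested assumptions about the time trend and about how reactivity builds up, and no such analysis is planned.

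**What would identify R.** A group with surveys but no FMI, alongside an unsurveyed wait list, raises the rank to 3 of 3. The plan has no such group under either reading.

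**Recall window.** Three descriptions sit side by side:

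- Section 10.3, Bi-Weekly Follow-Up Assessment: "participants will report on any occasion since the last assessment that the participant was out with the target friend in a social setting"
- Section 10.3, sexual assault measure: outings in the week before
- Section 16.1 and SAP, growth models: protective behaviours in the week before the intervention

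None says which window applies to the wait list's week-12 assessment.

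**The case against.** The strongest reply is that the Stage 3 aim and the six-wave model show that bi-weekly wait-list surveys were intended, so the FMI effect is not confounded. That may be so. The explicit schedule says otherwise, and the two need reconciling. The reply also does not rescue the reactivity statement, because survey effects then cancel from the arm comparison.

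A second reply is that the crossover does vary assessment history with the FMI held fixed, since wait-list women reach their FMI with one more full assessment behind them. This is true. But the comparison is mixed with 12 weeks of elapsed time, says nothing about the bi-weekly surveys, and is not planned. Likewise, reactivity to the shared baseline assessment is balanced between arms but not estimated.

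Three stronger readings are tempting, and the documents do not support them:

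- **Every randomised analysis is biased by five extra surveys.** The SAP's first model uses the first post-intervention assessment, before which FMI women have completed no earlier bi-weekly survey. If wait-list week 12 is the comparator there, the difficulty is timing, not survey load.
- **The week-12 recall is 12 weeks in one arm and 2 in the other.** That would follow only if the wording under the bi-weekly heading carried over to the wait list's week-12 assessment. Other sections use one week, so the window is unsettled.
- **Surveying the wait list would make reactivity estimable.** It would show reactivity plus time.

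It is also fair that this is a pilot focused on feasibility, and that the protocol promises only that reactivity can be examined, not that it has been.

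**Conclusion.** The reactivity statement is unsupported under both readings of the schedule. That conclusion is structural and does not depend on alpha, power, variance or dropout. The confounding of the FMI with survey load is conditional: it holds for a week-12 contrast if the wait list is assessed only at baseline and week 12, and disappears if it is surveyed bi-weekly.

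The size is unknown, because the documents give no reactivity figure. For illustration only, assume that five extra surveys shift protective behaviours by 0.1 to 0.3 SD and that the apparent effect is 0.5 SD. The share due to surveys is then 0.1 / 0.5 = 20% to 0.3 / 0.5 = 60%. Both inputs are assumptions; section 16.2 speaks only of moderate to large effects. The point should be corrected because the sentence is wrong as it stands and the minimum remedy is a change of wording.

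**What to change.** 1. **Reconcile the wait-list schedule** across Stage 3 Procedures, the Stage 3 aim, section 16.1 and the SAP.
2. **Preferred:** give wait-list dyads the same bi-weekly online surveys during the wait. This removes the survey-load confounding and supplies the data that the six-wave model needs. The week-12 assessment already exists, so five surveys are added: 24 dyads x 2 = 48 women; 48 x 5 x $20 = $4,800. Extending the $20 retention bonus adds up to 48 x $20 = $960, for a maximum of $5,760, plus reminders and some participant burden.
3. **Otherwise:** define the week-12 result in the protocol and SAP as the effect of FMI plus bi-weekly surveys. This costs wording only.
4. **In both cases:** delete or reword the reactivity claim. Under the preferred option, the text can say that survey load is balanced between arms and that the wait-list trend reflects reactivity and time together.
5. **Recall:** set one common recall window for the week-12 assessment in both arms and use it in every section that describes these measures.
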